### Table 6 – Algorithm for Assessing Disease Control

## Statistical Analysis Plan

| Overall Tumour Response at:          |                       |                      |                                      |
|---|-----------------------|----------------------|--------------------------------------|
| Disease Control
At Current Visit | Previous Visit | Current Visit | Next
subsequent
Visit |
| No  | PD                    | Any                  | Any                                  |
| No  | CR, PR, or SD         | PD                   | Any                                  |
| No  | CR, PR, or SD         | NE or Missing        | NE or Missing                        |
| Yes   | CR, PR, or SD         | NE or Missing        | CR, PR, or SD                        |
| Yes   | CR, PR, or SD         | CR, PR, or SD        | Any                                  |

In Part A and B, the number and percentage of patients who achieved disease control at even-numbered cycles will be summarized starting with Cycle 4 and at EOT. For Part B only, exact 2-sided 80% CIs will also be computed for DCR using the Clopper-Pearson method (Clopper and Pearson 1934).

### 8.3.6. Change in Tumour Size

The percentage change in tumour size from baseline to week 12 will be summarized for Part B only. However, the change in tumour size over time will be displayed for individual patients in both Part A and Part B. A time window of 1 week around the Week 12 visit will be applied, and it is recommended that any visits occurring 11 weeks or more after dosing are acceptable.

Tumour size is the sum of the longest diameters of a patient's TLs. The percentage change in TL size at Week 12 will be obtained for each patient by taking the difference between the sum of the longest diameters of the TLs at Week 12 and the sum of the longest diameters of the TLs at baseline divided by the baseline value and multiplied by 100. The baseline value for tumour measurements is the last evaluable assessment taken prior to first dose of study drug. The percentage change in tumour size will be summarized by treatment group using the Efficacy set.

If  $> 1/3$  of a patient's TL measurements are missing at Week 12, then the patient's TLs will not be included in the calculation of the percentage change in tumour size.

If  $\leq 1/3$  of a patient's TL measurements are missing at Week 12, then the results will be imputed (i.e., scaled up) using the sizes at the nadir visit to provide an estimated sum of diameters. This estimation is equivalent to comparing the week 12 sum of the longest diameters of the non-missing lesions to the nadir sum of diameters excluding the lesions

## Statistical Analysis Plan

with missing measurements. An example of scaling up is provided using the lesion lengths shown in Table 7.

Nadir is defined as the previous minimum where all lesions compared to those collected at baseline have a measurement. In the case where the result is being scaled up due to something other than just missing data, the nadir will fit all requirements. For example if tumours that received an intervention were not to be included in addition to missing tumours, then the nadir visit would require no missing data and no tumour interventions.

**Table 7 – Example of Scaling Up in Calculation of Change in Tumour Size**

| Lesion | Longest Diameter at nadir Visit (cm) | Longest Diameter at Week 12 Visit (cm) |
|--------|--------------------------------------|--|
| 1      | 7.2                                  | 7.1                                    |
| 2      | 6.7                                  | 6.4                                    |
| 3      | 4.3                                  | 4.0                                    |
| 4      | 8.6                                  | 8.5                                    |
| 5      | 2.5                                  | missing                                |
| Sum    | 29.3                                 | 26                                     |

In this example, the measurement for lesion 5 is missing at Week 12. The sum of the 4 non-missing lesion lengths at Week 12 is 26 cm. The sum of the lengths of the 4 corresponding lesions at the nadir visit was 26.8 cm. Scale-up gives an estimated Week 12 value of 28.4 cm as follows:

$$\text{Scaled-up Week 12 length} = (26 \times 29.3)/26.8 = 28.4$$

Consequently, assuming a baseline value of 30.4, the imputed percentage change in tumour size from baseline to Week 12 would be reported as:

$$\% \text{ Change in tumour size} = [100 \times (28.4 - 30.4)]/30.4 = -14.5\%$$

If a TL becomes too small to measure at Week 12, a value of 5 mm will be used in calculating the tumour size at Week 12, unless the radiologist has indicated and entered a smaller value that can be reliably measured.

The percentage change in TL size will be presented graphically using waterfall plots for each treatment group, with the percentage change in TL size for each patient shown as a separate bar and with the bars ordered from the largest increase to the largest decrease.

## Statistical Analysis Plan

Reference lines will be added to the waterfall plot at the +20% and the -30% change in tumour size levels, which correspond with the definition of disease progression and ‘complete or partial’ response, respectively. In the waterfall plots, patients whose change in TL size is based on imputation will be clearly identified by different-colored bars on the waterfall plot.

If the patient does not have a Week 12 visit, then a tumour assessment that is taken at 11 to 15 weeks may be used as the Week 12 measurement.

A similar plot will also be presented for each patient’s best percentage change (the maximum reduction from baseline or the minimum increase from baseline in the absence of a reduction from baseline based on all post baseline assessments) in TL size up to progression. Individual absolute total TL measurements, changes from baseline, and percent changes from baseline will be listed for each tumour assessment visit.

For both Part A and Part B, a series of spider plots will graphically present the percentage change in total TL size from baseline by study day for each patient, grouped by treatment arm.

### 8.3.7. Progression-free Survival (PFS)

Progression-free survival (PFS) is defined as the time (days) from the date of treatment allocation (Part A) or randomization to study drug (Part B) to the date of objective disease progression or death due to any cause, whichever occurs first. This definition will apply regardless of whether the patient withdraws from treatment or receives another anti-cancer therapy prior to progression.

The PFS time will be derived based using scan/assessment dates and not visit dates. PFS times will be derived using assessment dates from the “Tumour Assessment” CRF pages or, if needed, the date of death from the “Death” CRF page.

RECIST assessments/scans contributing towards a particular visit may be performed on different dates. The following rules will be applied:

- Date of progression will be determined based on the **earliest** of the dates of the component that triggered progression
- When censoring a patient for PFS, the patient will be censored at the **latest** of the dates contributing to a particular overall visit assessment

Patients who have not progressed or died at the time of the analysis will be censored at the time of the latest date of assessment from their last evaluable RECIST assessment.

## Statistical Analysis Plan

However, if the patient progresses or dies after two or more missed visits, the patient will be censored at the time of the latest evaluable RECIST version 1.1 assessment. If the patient has no evaluable visits or does not have baseline date, the patient will be censored at Day 0 (i.e., excluded from the K-M analysis), unless the patient dies within 2 visits of baseline in which their date of death will be used to derive PFS. Two visits will be considered to have been missed if more than 126 days have passed since the patient's last visit.

PFS will be analyzed for all evaluable patients using a K-M survival analysis. The distribution of PFS times assessed by RECIST version 1.1 criteria will be displayed graphically by treatment group. The number of events, percentiles for the PFS (25%, 50% (median), and 75% percentiles), and the proportion of patients who are progression-free at 1, 2, 3, and 4 months will be summarized by treatment group. For Part B only, two-sided 80% CIs will be provided for the median PFS times (Brookmeyer and Crowley, 1982), which can be reported using SAS LIFETEST Procedure with CONFTYPE=LINEAR. The 80% CIs for median PFS is the set of all  $t$  which meets  $|ES(t)-0.5|/se(ES(t)) \leq z_{0.9}$ , where  $ES(t)$  is the estimated survival function and  $se(ES(t))$  is the standard error of  $ES(t)$ .

If there is a sufficient number of PFS events observed in Part B, the relationship between biomarkers and PFS may be explored using Cox regression.

### 8.3.8. Overall Survival (OS)

Overall survival (OS) is defined as the time from the date of the treatment allocation (Part A) or randomization to study drug (Part B) to the date of death from any cause. OS will be estimated using K-M methodology and the Efficacy Set. Any subject not known to have died at the time of analysis will be censored based on the last recorded date that the subject was known to be alive. This date is the latest of the last known tumour assessment, the last date of collection of clinical laboratory or vital sign data, or the last date of telephone contact with the subject.

In dose-expansion Part B, some patients may be allowed to move from a monotherapy arm to a combination arm during the trial. The survival times for these patients will be censored at the date immediately prior to the date of the first dose of the combination drug.

The distribution of OS in the Efficacy Set will be displayed graphically by treatment group. The number of events and estimates for the 25%, 50% (median), and 75% percentiles for OS will be summarized by treatment group. For Part B only, two-sided 80% CIs will be provided of the median OS estimates (Brookmeyer and Crowley, 1982).

## Statistical Analysis Plan

### 8.3.9. Survival at 12 Months (OS-12)

Overall survival at 12 months (OS-12) is defined as the percentage of patients surviving at 12 months after randomization to study drug.

Should a patient's vital status at 12 months be unknown, the patient will be considered to be deceased when estimating OS-12. This approach is a conservative one and assumes that patient loss is related to mortality.

An exact two-sided 80% CI for OS-12 will be computed using the Clopper-Pearson method (Clopper and Pearson 1934). Analysis of this secondary endpoint will use the Safety set.

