4.2.3 End-of-treatment evaluations and follow-up

EOT evaluations, including safety and tumor assessments, shall be performed as soon as possible following the decision to discontinue treatment (see the study event overview, [Table 5](#)).

In addition, patients should be followed up for at least 28 days (+7 days) after the last dose of study treatment for any new reports of AEs, SAEs, and concomitant medications.

Safety follow-up for IM will continue for all patients treated with MEDI4736 for 90 days (± 7 days) after the last dose of MEDI4736 or until the initiation of subsequent anticancer therapy.

Patients who discontinued treatment for reasons other than PD will continue to undergo tumor assessments every 2 months (± 7 days) until PD is noted. All patients will be followed for subsequent anticancer therapy every 2 months (± 7 days) and will also be followed for OS every 2 months (± 7 days) from the date of randomisation to the date of death due to any cause, assessed for approximately 40 months. The patients will be censored on the date of last follow-up visit.

The status of “ongoing,” “withdrawn from the study,” and “lost to follow-up” for patients at the time of an OS analysis should be obtained by the site personnel through checking the patient notes, hospital records, contacting the patient’s general practitioner, and checking publicly available death registries. If the patient has actively withdrawn consent to the processing of their personal data, the vital status of the patient can be obtained by site personnel from publicly available resources where it is possible to do so under applicable local laws.

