6.12 Expected start and end of study

The study started on 05 Aug 2015 (first patient screening visit). The data cut-off for the primary endpoint will be the 28 Feb 2020 (6 months + 90 days follow up after the last patient recruited and started IP). Data analysis will be performed, and a CSR will be written based on this data cut-off.

Any patients still receiving IP at the time of this data cut-off will be able to continue to receive IPs within the current study, through a continued treatment period, while they are in the Investigator's opinion, deriving clinical benefit and not fulfilling discontinuation criteria. During this continued treatment period, assessments will revert to the standard of care for each individual site. Data will not be entered into the clinical study database after the data cut-off date. During this continued treatment period, patients will continue to be monitored for all SAEs up to 28 days after the last dose of IP. Paper based SAE reporting will be used for any SAEs identified after the data cut-off. SAE data will be entered in to the AstraZeneca's global safety database. All SAEs, overdoses and pregnancies will be reported until 28 days after last dose. The IVRS system will be closed following the data cut-off, and sites will manually order IP. The IP dispensation and reconciliation will be handled by the study site at each patient's visit. The IP accountability information must still be collected until all patients have completed treatment. After the data cut-off for the CSR, individual study sites will be closed once their final patient completes the 28-day follow-up visit. The continued treatment period will remain available to patients until the last patient completes treatment and has his or her 28-day safety follow-up visit. The Last Subject Last Visit is defined as the date of the last patient's 28-day safety follow-up visit.

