Progression-free survival is defined as the time from start of treatment (Cycle 1, Day 1) until the date of objective disease progression or death (by any cause in the absence of progression) regardless of whether the patient withdraws from therapy or receives another anticancer therapy before progression. Patients who have not progressed or died at the time of analysis will be censored at the time of the latest date of assessment from their last evaluable RECIST version 1.1 assessment. However, if the patient progresses or dies after 2 or more missed visits, the patient will be censored at the time of the latest evaluable RECIST version 1.1 assessment. If the patient has no evaluable visits or does not have baseline data, he/she will be censored at 0 days unless he or she dies within 2 visits of baseline.

The PFS time will always be derived based on scan/assessment dates not visit dates.

RECIST version 1.1 assessments/scans contributing towards a particular visit may be performed on different dates. The following rules will be applied:

- Date of progression will be determined based on the earliest of the dates of the component that triggered the progression
- When censoring a patient for PFS the patient will be censored at the latest of the dates contributing to a particular overall visit assessment

Overall survival

Overall survival is defined as the time from the date of Cycle 1, Day 1 until death due to any cause. Any patient not known to have died at the time of analysis will be censored based on the last recorded date on which the patient was known to be alive.

Survival at 12 months

Patients who are alive 1 year following the beginning of treatment are said to have survived 12 months. Patients whose vital status is unknown at 12 months will be censored at the last date that the patient was known to be alive.

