Duration of response will be summarised using KM based methods and will include minimum, 25th percentile, median, 75th percentile, and maximum. Kaplan-Meier plots will also be presented. Only patients who achieve an overall response will be included in this analysis.

Durable response rate

Durable response rate is defined as the percentage of patients who have a durable response. The denominator for the durable response rate will be the efficacy analysis set (see Section 8.3).

Progression-free survival

Progression-free survival will be analysed using KM methods in an exploratory manner. Summaries of PFS (number of events, medians, quartiles, and proportion progression free at 1, 2, 3, and 4 months after the first dose of IP) will be presented.

If there is a sufficient number of PFS events observed in the study, the relationship between biomarkers and PFS may be explored using Cox regression.

Overall survival

Summaries of OS (n, deaths, medians, quartiles), and KM plots will be provided as appropriate.

If there is a sufficient number of OS events observed in the study, the relationship between biomarkers and OS may be explored using Cox regression.

Proportion of patients surviving at 12 months

The proportion of patients surviving at 12 months will be presented. An exact 2-sided 80% CI will be computed using the method of Clopper and Pearson (Clopper and Pearson 1934). In addition, OS at 12 months will be estimated using the survival probability at 12 months from the KM analyses.

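### As written, the SAP 8.3.9 rule that unknown 12-month status counts as death also catches patients alive at data cut-off with under 12 months of follow-up, and the departure from protocol 8.9 and 8.10 is not recorded

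*SAP*

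**What the plan says.** **SAP 8.3.9 (OS-12).** OS-12 is the percentage of patients surviving 12 months after randomisation. If a patient's "vital status at 12 months be unknown, the patient will be considered to be deceased when estimating OS-12". The section defends this in one sentence: "This approach is a conservative one and assumes that patient loss is related to mortality". It attaches an exact two-sided 80% Clopper-Pearson interval and specifies no KM estimate.

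**Protocol 8.9.** The same situation is handled the other way: "Patients whose vital status is unknown at 12 months will be censored at the last date that the patient was known to be alive".

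**Protocol 8.10.** A crude proportion with an exact 80% Clopper-Pearson interval is planned and, in addition, "OS at 12 months will be estimated using the survival probability at 12 months from the KM analyses".

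**Protocol 6.12.** The data cut-off is "28 Feb 2020 (6 months + 90 days follow up after the last patient recruited and started IP"). It continues: "Data analysis will be performed, and a CSR will be written based on this data cut-off", and "Data will not be entered into the clinical study database after the data cut-off date". The section calls this the cut-off for the primary endpoint. Protocol 4.2.3 plans survival follow-up to the "date of death due to any cause, assessed for approximately 40 months", but neither document gives a later cut-off for survival.

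**SAP 8.3.8 (OS).** A patient not known to have died is censored at the last date known alive. The outputs are the curve, the number of events, the quartiles and the median with its interval; a 12-month probability is not listed.

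**SAP 13.** The only recorded change from the protocol is the added wording about important protocol deviations in the PK, PD and Efficacy set definitions.

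**The concern.** A patient can have unknown status at month 12 for two different reasons. One is loss to follow-up, where assuming death is a defensible cautious convention. The other is that the database closed before month 12, which says nothing about prognosis. The SAP's justification covers only the first, while its rule covers both. Under the literal rule a late starter can never count as a survivor, whatever happens, so every late starter lowers the estimate. The Clopper-Pearson interval cannot show this, because it treats those patients as observed deaths.

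The same patient would then be censored alive in the OS analysis and counted dead in OS-12, within one report. The bias would also follow entry date, so arms that recruited last would look worse beside arms that recruited earlier for a reason unrelated to treatment.

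Separately, the protocol planned an estimator that handles censoring, the SAP leaves it out, and the reader of the SAP is not told.

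**Working it through.** The plan states no expected value, precision or power for OS-12, so there is no figure of its own to reproduce. The check has three parts.

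**1. Can such patients exist at the cut-off?** Inputs are from protocol 6.12.
- 28 Feb 2020 minus 90 days is 30 Nov 2019; minus 6 months is 30 May 2019. That is the implied last start of treatment.
- 30 May 2019 to 28 Feb 2020 is 274 days, and 274/30.4375 = 9.0 months.
- Twelve months of follow-up needs a start by about 28 Feb 2019. The late-start window, 28 Feb to 30 May 2019, is 91 days.

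So at least the last patient recruited falls in the window. These dates count from start of treatment. The SAP counts OS-12 from randomisation, which Arms B7 and B8 do not have.

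**2. How large could the effect be?** Let p be true 12-month survival and m the number of late starters in an arm of 48 (the planned size of B7 and of B8). A late starter is either a known death or scored as one, so the expected reported value is p × (48 − m)/48, and the bias is −p × m/48. Coverage of the 80% interval is exact: X ~ Binomial(48 − m, p), with the Clopper-Pearson interval computed on X out of 48. Both p and m are assumptions; neither is in the documents.

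| m | p = 40%: reported / coverage | p = 50%: reported / coverage | p = 60%: reported / coverage |
|---|---|---|---|
| 0 | 40.0% / 86% | 50.0% / 81% | 60.0% / 86% |
| 1 | 39.2% / 86% | 49.0% / 81% | 58.8% / 86% |
| 2 | 38.3% / 85% | 47.9% / 80% | 57.5% / 86% |
| 3 | 37.5% / 83% | 46.9% / 78% | 56.3% / 83% |
| 5 | 35.8% / 79% | 44.8% / 71% | 53.8% / 76% |
| 8 | 33.3% / 68% | 41.7% / 56% | 50.0% / 57% |
| 16 | 26.7% / 27% | 33.3% / 11% | 40.0% / 6% |

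The m = 16 row comes from one accrual assumption. Suppose B8 filled all 48 places evenly from 24 Aug 2018 (Amendment 9, the first submitted version containing B8) to 30 May 2019. That is 279 days, and 48 × 91/279 = 15.7. It also assumes that B8 recruited the last patient. None of this is documented.

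With censoring and KM at 12 months instead, simulation gave a mean estimate of 0.498 to 0.501 and coverage of 79% to 81% for m = 1 to 16 (4,000 trials per m, n = 48, exponential survival with true OS-12 of 50%, late starters censored uniformly at 9 to 12 months, log-log 80% interval). That check contains administrative censoring only.

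**3. Is the departure recorded?**

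| Point | Protocol | SAP |
|---|---|---|
| Unknown status at 12 months | Censor at last date known alive (8.9) | Count as dead (8.3.9) |
| KM 12-month probability | Planned (8.10) | Not specified (8.3.8, 8.3.9) |
| Crude proportion, exact 80% interval | Planned (8.10) | Kept (8.3.9) |
| Change listed | – | Neither (13) |

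**The case against.** **The rule's own rationale limits it.** The SAP speaks of patient loss, and a patient alive at cut-off is not lost. Protocol 4.2.3 also has sites trace vital status through records and death registries, which fits unknown meaning untraceable. This is probably what the authors meant, and a reader should not infer that they intend to score living patients as dead. It does not remove the point: the operative sentence has no exception, and a programmer would code the sentence.

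**The size is undocumented.** This stands. A reader might take 33.3% with 11% coverage as a forecast for B8. It is not one: it rests on assumed even accrual from an amendment date, a full arm and the last patient being in B8, and B8 also carried a futility rule from its 15th patient. With one to three late starters the effect is negligible.

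**Most arms may be untouched.** Protocol 4.2.2 describes B1 to B6 as already enrolled and B7 and B8 as still to enrol. That suggests late starters sit mainly in B7 and B8, although no accrual dates by arm are given. The documents do not support an endpoint-wide bias.

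**The protocol is itself incomplete.** Its crude proportion cannot use a censored value, and 8.10 does not say how one enters. The SAP fills that gap with a disclosed convention. That is fair for the crude proportion, but 8.9 still says to censor, and the KM estimate that would do so is gone. The kept OS curve would let a reader take off a 12-month value, and table shells sit in a separate document, but the SAP text does not plan the estimate.

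**KM is not a clean remedy everywhere.** This also stands. SAP 8.3.8 censors monotherapy patients at the switch to combination, which follows confirmed progression. That censoring is likely informative, so a 12-month KM value from that analysis could be too high in B5 and B6. The simulation above does not cover it.

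**Conclusion.** The point holds as a discrepancy in the text: the rule is wider than its justification, the cut-off makes the uncovered case possible, and two departures from the protocol are missing from Section 13. The unrecorded departures hold even if no patient is affected.

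The numerical consequence is open. The direction is certain (downward), and the size is p × m/48 in an arm of 48, with m unknown. It may be negligible or material. The window assumes that the 28 Feb 2020 cut-off applies to OS-12; a later survival cut-off would shrink or remove it, but none is stated.

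A reader might infer that the trial's main conclusion is at risk. The documents do not support that. The primary endpoint is objective response, OS-12 is descriptive and drives no decision rule, SAP Section 8 plans no inferential comparison between groups, and the KM curve for OS is kept. This should be fixed as a reporting error in a named secondary endpoint.

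**What to change.** In SAP 8.3.9:
- Restrict counting unknown status as death to patients lost to follow-up whose start date allowed 12 months before the cut-off.
- Limit the Clopper-Pearson proportion to patients with 12 months of potential follow-up, selected on start date alone. Late starters who died must leave the denominator along with those alive; otherwise the proportion is again biased downward.
- Restore the KM 12-month survival probability from protocol 8.10 with an 80% interval, censoring patients alive at cut-off at the last date known alive.
- For B5 and B6, compute that estimate without censoring at the switch to combination, in line with the follow-up analysis in SAP 11.10.3, or show it next to the crude proportion.
- State which cut-off date applies to OS-12.

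In SAP 13, list the OS-12 handling as a change from the protocol.

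A separate consistency point: SAP 8.3.9 uses the Safety set for OS-12, while SAP Table 3 assigns it to the Efficacy set. The two should be reconciled.

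Cost: a rewritten 8.3.9, one line in Section 13 and one added row in the OS table. No new data are needed.
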